### 13.2 Definition of Evaluable Patients

All measurements should be taken and recorded in metric notation using a ruler or calipers. All baseline evaluations will be performed as closely as possible to the beginning of treatment and never more than 2 weeks before the beginning of the treatment.

The same method of assessment and the same technique should be used to characterize each identified and reported lesion at baseline and during follow-up. Imaging-based evaluation is preferred to evaluation by clinical examination when both methods have been used to assess the antitumor effect of treatment.

**Clinical Lesions:** Clinical lesions will only be considered measurable when they are superficial (e.g., skin nodules, palpable lymph nodes). In the case of skin lesions, documentation by color photography including a ruler to estimate the size of the lesion is recommended.

**Chest X-rays:** Lesions on chest X-ray are acceptable as measurable lesions when they are clearly defined and surrounded by aerated lung. However, CT is preferable.

**Conventional CT and MRI:** These techniques should be performed with cuts of 10mm or less in slice thickness contiguously.

**Spiral CT:** Spiral CT should be performed using a 5mm contiguous reconstruction algorithm.

**Ultrasound:** When the primary endpoint of the study is objective response evaluation, ultrasound should not be used to measure tumor lesions. It is, however, a possible alternative to clinical measurements of superficial palpable lymph nodes, subcutaneous lesions, and thyroid nodules. Ultrasound may also be useful to confirm the complete disappearance of superficial lesions usually assessed by clinical examination.

### **13.3 Time to Recurrence of Disease (TTR)**

Time to recurrence will be measured from the treatment start date (date of first dose) to either the date the patient is first recorded as having disease recurrence (even if the patient went off treatment because of toxicity), or the date of death if the patient dies due to any causes before recurrence.

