**Objective(s):****Primary Objectives:**

- To assess time to recurrence (TTR) following the administration of bi-shRNAfurin and GMCSF autologous tumor cell (Vigil™) vaccine.

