### **Follow Up Assessments**

If the Vigil™ vaccine is discontinued (for reasons such as completion of all available doses of vaccine, intolerable toxicity, treatment interruption of more than 4 weeks, intercurrent illness, protocol deviation at PI's discretion), the patient will be contacted by phone every 3 months after the end of study visit for:

- disease status
- request of medical records, when applicable (laboratory findings, radiological scans, and progress report)
- documentation of 2nd line therapy
- recording of response and duration of response to that therapy
- survival
- assessment of any additional cancer treatments)

**Note:** Patients who die or withdraw consent are considered **off study** and no further information except survival data will be collected.

Based on findings during the study or during the follow up portion of the trial, Gradalis may request for additional blood and / or tissue samples from the research participant. Collection of whole blood (40ml) and / or tissue samples (via biopsy or clinically indicated surgical removal) will be **optional** and used to study the effects of the study agent (included, but not limited to testing of biomarkers, predictors or biological responses, toxicity, relationship between genotype and study agent responses).

Should Gradalis request for additional blood or tissue, the clinical site will present the option of the procurement to the participant and obtain written informed consent.

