## 8.0 EVALUATION OF TUMORS

### 8.1 Disease Evaluation

Disease recurrence will be evaluated in this study using the Response Evaluation Criteria in Solid Tumors Version 1.1 (RECIST) (unidimensional measurement) of the tumor lesions are used in the RECIST criteria (Eisenhauer, Therasse et al. 2009).

Disease recurrence is defined as the appearance of any measurable or evaluable lesion or as asymptomatic CA-125 levels greater than 35 U/mL at two consecutive measurements, at least one month apart. The time to recurrence is measured from date of first treatment until the first date that recurrence is objectively documented whether local, regional, or distant.

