## 13.0 DATA EVALUATION

### 13.1 Statistics and Estimated Sample Size

The primary objective of this study is to investigate whether maintenance Vigil™ vaccine after a clinically defined complete response to induction platinum/paclitaxel chemotherapy results in prolonged time to recurrence (TTR) compared with standard of care observation. TTR was used for the purpose of sample-size estimation. Based on prior published experience (Markman, Liu et al. 2003), the median RFS after a clinical complete response to induction therapy for the control arm was estimated to be approximately 16 months for those with stage IV or suboptimal (> 1 cm residual) stage III disease and 24 months for stage III patients with optimal (< 1 cm residual) disease. Given an average RFS of 24 and 16 months, respectively, a 10% increase in RFS (i.e. TTR) would provide adequate statistical power to support expanding the study (Table 6). This analysis was performed using a statistical power calculator (<http://www.dssresearch.com/KnowledgeCenter/toolkitcalculators/statisticalpowercalculators.aspx>) to conduct a 1-tail test of a sample average in comparison to the historical value, a standard deviation of 1.0, and an alpha error level of 5%. In order to expand the protocol treatment base and increase the rate of accrual while maintaining the objectives of the protocol, the study, which was initially limited to patients with stage IIIC ovarian cancer, is being expanded to patients with Stage III/IV disease. In the SEER database: 1988-2001(Kosary 1988-2001), women with Stage IIIC disease comprised 19.4% of the ovarian cancer population; those with Stage III inclusive, 35.3%; and those with Stage IV, 31.7%. Thus, the eligibility expansion increases the base catchment population from 19.4% of women with ovarian cancer to 67% of which only a subset will meet protocol criteria.

In the completed Phase I study of Vigil™ vaccine in patients with solid tumors experiencing progressive disease following prior therapy, 50% of patients with serial assessments (n=18) demonstrated conversion from  $\gamma$ IFN ELISPOT

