### **13.4 Time to Treatment Failure**

Time to treatment failure will be measured as the date from when the patient started treatment (first dose) to the date the patient is withdrawn due to: AE(s), progressive disease/insufficient therapeutic response, death, failure to return, refused treatment/did not cooperate/withdrew consent, or started a new

treatment. Patients who do not fail treatment will be censored at the date of last follow-up.

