### **13.5 Survival**

Survival will be measured, as the time from start of treatment to the date of death or the last date the patient was known to be alive.

Long-term survival information will be collected.

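### TTR, treatment failure and survival are timed from first dose, which leaves randomized observation patients without a time zero, and sections 8.1 and 13.3 disagree on whether death is a TTR event

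*Combined protocol and SAP*

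**What the plan says.** Origin. Section 13.3, where the thing recorded is recurrence: "Time to recurrence will be measured from the treatment start date (date of first dose) to either the date the patient is first recorded". Section 8.1: "The time to recurrence is measured from date of first treatment until the first date that recurrence is objectively documented". Section 13.4 starts time to treatment failure at first dose. Section 13.5: "Survival will be measured, as the time from start of treatment to the date of death" or the date last known alive.

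End of TTR. Section 13.3 adds a second terminating event: "or the date of death if the patient dies due to any causes before recurrence". Section 8.1 mentions recurrence only.

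Censoring. Section 13.4 has a rule, "Patients who do not fail treatment will be censored at the date of last follow-up", and 13.5 implies one. Section 13.3 has none. The follow-up text in 6.6 says that after death or withdrawal of consent "no further information except survival data will be collected".

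Comparison. The Synopsis and section 3.1 give the primary objective without a comparator: "To assess time to recurrence (TTR) following the administration of" the vaccine. Section 13.1 words it as whether maintenance vaccine "results in prolonged time to recurrence (TTR) compared with standard of care observation". Table 6 is laid out as a 2:1 randomized comparison with an observation column, and the text after it plans summaries of second-line response in both groups. The Synopsis says new patients are no longer randomized, and cites p=0.005 for time to relapse in patients already randomized to Vigil or no Vigil.

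**The concern.** A patient on observation never receives a dose, so a clock that starts at first dose cannot be started for her. A patient assigned to Vigil who relapses, withdraws or becomes ineligible before dose 1 has no start either and drops out of the analysis. Any comparison run under the stated rule would therefore need an origin for one arm that this version does not supply, and would set selected Vigil patients (those who reached dose 1) against the control group. Leaving that open is awkward once a between-arm result has been seen.

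The death question is independent of the comparison. If the two sections that define the primary endpoint disagree on what counts as an event, the event set for every patient, including those enrolled after randomization stopped, depends on which section is followed.

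**Working it through.** **1. The definitions side by side**

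| Section | Start | End | Death without recurrence | No event |
|---|---|---|---|---|
| 8.1 (TTR) | first treatment | documented recurrence | not mentioned | not mentioned |
| 13.3 (TTR) | first dose | recurrence or death | event | not mentioned |
| 13.4 (treatment failure) | first dose | withdrawal for listed reasons | event | censored at last follow-up |
| 13.5 (survival) | start of treatment | death | event | date last known alive |

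**2. The start rule applied to each kind of patient**

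- Randomized to Vigil and dosed: time zero exists.
- Randomized to Vigil, never dosed: no time zero; left out.
- Randomized to observation: no time zero under any of the four sections. The looser wording in 8.1 does not help, because 13.3 equates treatment start with the first dose.
- Enrolled after randomization stopped, and dosed: time zero exists, and first dose is a workable origin for describing this cohort.

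The gap is therefore confined to patients already randomized, and matters only if they are compared by arm.

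**3. Is that comparison still in the plan?**

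The current text points both ways. Against: the stated objectives name no comparator, and the power text in 13.1 describes a one-tailed test of a sample average against a historical value. For: the objective as worded in 13.1, the layout of Table 6, and the planned summaries by group.

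Table 6 states power 1.0 in each stratum (n = 30, SD 1.0, one-sided 5%, gains of 26.4 − 24 = 2.4 and 17.6 − 16 = 1.6 months; SD taken to be in months). It reproduces on either reading:

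- One sample against a fixed value: noncentrality 2.4 × √30 = 13.1 and 1.6 × √30 = 8.8; power 1.00 and 1.00.
- Two samples, 20 and 10 patients, normal approximation: SE = √(1/20 + 1/10) = 0.387; 1.6/0.387 − 1.645 = 2.49, power 0.99; 2.4/0.387 − 1.645 = 4.55, power 1.00.

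So the printed power does not show which design is meant, and it uses no time origin.

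**4. The event rule applied to one patient**

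Take a patient who dies without documented recurrence. Under 13.3 she has an event on the date of death. Under 8.1 she has none, and neither section says when to censor her.

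**5. Size**

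Three quantities would be needed: the number randomized and never dosed, the wait from randomization to dose 1, and the number of deaths before recurrence. None is given. The direction is also open. Starting only the Vigil clock later than randomization shortens Vigil times, which works against the vaccine. Excluding Vigil patients who relapse before dose 1 works in its favour.

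**The case against.** The strongest reply is that the trial is now a single-arm, open-label study, for which first dose is the proper origin, and that the observation wording is left over from before the amendment. For patients enrolled from now on this stands. It does not dispose of the point, because the statistical section still makes the comparison the primary objective and the randomized patients exist. It does make the start-date consequence conditional on the comparison being kept.

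Second, a between-arm analysis has already been run, so some control origin was used. That is fair. A reader might infer that the p=0.005 result rests on an arbitrary or post hoc control start. The documents do not support this: they do not say which origin was used, and an earlier version may have fixed one.

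Third, a reader might set the permitted interval between chemotherapy and dose 1 against the planned gains and conclude that the mismatch could erase them. No passage times controls from the end of chemotherapy. The control medians in 13.1 are a literature planning benchmark counted from clinical complete response, not an endpoint rule, so that calculation has no footing here.

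Fourth, never-dosed patients may be few: four manufactured vials are required for registration, so manufacturing failure should come before assignment. This is reasonable, but other reasons for not starting remain and no count is given.

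Fifth, the wait may be short. Section 13.2 limits baseline evaluations to 2 weeks before treatment. If they precede registration and are not repeated (an inference, since 6.6 allows 4 weeks for some items), the wait is at most 14/30.44 = 0.46 month, which is 29% of 1.6 and 19% of 2.4 months. That suggests a modest shift but does not establish it.

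Finally, 13.3 is the dedicated endpoint section and is explicit on death, so aligning 8.1 is a short edit. Agreed; the edit is still needed.

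**Conclusion.** The point holds in two parts. First, this version times TTR, treatment failure and survival only from first treatment or first dose. While 13.1 keeps a comparison with observation, that rule cannot be applied to one arm and omits assigned patients who were never dosed. If the comparison is dropped, this part largely goes away, but 13.1, Table 6 and the text after it must then change. Second, and without any condition, 8.1 and 13.3 give the primary endpoint conflicting event definitions for every patient.

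Neither effect can be sized from the documents, and the net direction of the first is unknown. Nothing here shows that the reported result is wrong. The missing censoring sentence in 13.3 is a lesser omission. It has practical weight because section 1.3 puts relapse among complete clinical responders at about 75%, which leaves about 100 − 75 = 25% for whom no recurrence is expected.

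**What to change.** 1. If the comparison with observation is kept, measure TTR, time to treatment failure and survival from the date of randomization, in the assigned arm, for all patients already randomized (13.3, 13.4, 13.5, and 8.1 to match). Disclose that this origin was set after the p=0.005 result was seen.
2. Keep first dose as the origin for the Vigil-only description.
3. Make 8.1 agree with 13.3: the event is recurrence or death from any cause.
4. Reconcile 13.1, Table 6 and the text after it with the objectives in the Synopsis and 3.1, and state whether the comparison with observation is primary.
5. While editing 13.3, add censoring at the last disease assessment without recurrence, as a minor completion.

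Do not give controls a constructed start such as randomization plus the median wait to dose 1. It uses post-randomization data and leaves controls who recur before that date with negative times or excluded.

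Cost: wording in five sections (8.1, 13.1, 13.3, 13.4, 13.5) and re-derivation of the endpoints for the randomized patients. Section 6.1 describes a confirmed registration/randomization step, so the dates should be retrievable; this is an assumption. Counting the wait before dose 1 slightly dilutes a true effect.

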### **13.4 Time to Treatment Failure**

Time to treatment failure will be measured as the date from when the patient started treatment (first dose) to the date the patient is withdrawn due to: AE(s), progressive disease/insufficient therapeutic response, death, failure to return, refused treatment/did not cooperate/withdrew consent, or started a new

treatment. Patients who do not fail treatment will be censored at the date of last follow-up.

### **13.5 Survival**

Survival will be measured, as the time from start of treatment to the date of death or the last date the patient was known to be alive.

Long-term survival information will be collected.

## **14.0 STUDY RECORDS**

### **14.1 Documentation**

A log of all patients evaluated for this protocol must be maintained at each site. Patients excluded from admission will be provided with a clear explanation of the specific reasons why they have been excluded from the study. Patients who are included will be assigned a patient identification number.

For each patient treated with the study drug(s), the Research Coordinator is required to prepare and maintain case histories that include all observations and other data pertinent to the investigation. This will include all source documents needed to verify the accuracy of all observations and other data contained in the CRFs on each study patient.

The Investigator or his/her designee is required to retain the records related to the trial for a period of 2 years following the date a marketing application is approved for the indication being investigated. If no application is to be filed or if the application is not approved for such indication, the records must be retained until 2 years after the investigation is discontinued and the regulatory agencies are notified.

The Investigator shall retain study drug disposition records and source documents for the maximum period required by the country and institution in which the study will be conducted, or for the period specified by Gradalis, which ever is longer. The Investigator must contact Gradalis, Inc. prior to destroying any records associated with the study.

If the Investigator withdraws from the study (e.g., relocation, retirement), the records shall be transferred to a mutually agreed upon designee (e.g., another investigator, IRB). Notice of such transfer will be given in writing to Gradalis, Inc.

#### **14.2 Case Report Form (CRF) Procedures**

CRFs will be supplied by Gradalis, Inc. for recording all data from each patient. CRFs must be typewritten or printed legibly using black ballpoint pen or completed electronically. The investigator or his/her designee is responsible for recording all data relating to the trial on the CRFs. The investigator must verify that all data entries on the CRFs are accurate and correct.

If an item is not available or is not applicable, it should be documented as such; no blank spaces should be left on a CRF.

**APPENDIX A**  
**ECOG Performance Status Scale**

ECOG Performance Status Scale	
Grade	Description
0	Normal activity. Fully active, able to carry on all pre-disease performance without restriction.
1	Symptoms, but ambulatory. Restricted in physically strenuous activity, but ambulatory and able to carry out work of light or sedentary nature—(e.g., light housework or office work).
2	In bed <50% of the time. Ambulatory and capable of all self care, but unable to carry out any work activities; up and about > 50% of waking hours.
3	In bed >50% of the time. Capable only of limited self-care, confined to bed or chair >50% of waking hours.
4	100% bedridden. Completely disabled; cannot carry out any self care; totally confined to bed chair.
5	Dead

## APPENDIX B

## Schedule Of Assessments

Procedure	Prestudy	Screening	Monthly (q 28±3 days)	End of TX	Follow-Up
Informed consent	X	X			
Phone Contact	X 				
Medical History	X	Interval Medical History within 4 weeks			
Physical Examination	X	X	X	X	
Toxicity (adverse events)			X	X	
Concomitant medications		X	X	X	
Performance Status	X	X	X	X	
Clinical Tumor Assessment		X	X	X	
Radiological Tumor Assessment (abdomen/pelvis) 	within 6 weeks	within 4 weeks		X	
CBC with differential	X	X	X	X	
HIV testing, if applicable		X			
CA-125 tumor assessment 	X	X	X	X	
Serum Chemistry	X 	X	X	X	
Immune Function Analysis	At tissue procurement and prior to the 1st and 3 rd cycles of chemotherapy post debulking	X	Months 2, 4, 6 prior to vaccine administration	X	
Urinalysis		X			
EKG		X			
Vaccine administration 			X		
Injection Site Assessment			Day 2 only		
FACT-O 		X	X		
Survival Status	X			X	X 

 Following tissue procurement, patients will be contacted every 6 weeks ±2 weeks to assess interest / eligibility of the main randomized portion of the trial and survival status.

 Radiographic assessments taken at baseline, ≤ 1 week prior to Cycle 4, at SOC intervals, and when CA-125 >35U/mL.

 CA-125 taken at baseline, monthly for the first year, every 3 months ± 2 weeks for the second and third year.

 Obtain from medical records from standard preoperative hematology and chemistry panels.

 The patient will be observed for at least 30 minutes (with a 10% window) following vaccination. During this observation period, vital signs will be taken every 10 minutes (with a 10% window).

 FACT-O assessment will be collected at baseline, Month 3, Month 6, Month 12, and Month 18.

 After EOT, subjects will be contacted by phone quarterly for disease status, medical records (when applicable), documentation of 2nd line therapy and recording of response and duration of response to that therapy, additional cancer treatments as well as survival.

**APPENDIX C****NCI Common Toxicity Criteria For Adverse Events (CTCAE), Version 3.0**

**Publish Date: MARCH 31, 2003**

As of April 02, 2003 NCI has introduced version 3.0 of the Common Toxicity Criteria for Adverse Events. These may be obtained at the following web link <http://ctep.cancer.gov/reporting/ctc.html> or on the Mary Crowley CTMS.

**DO NOT USE CTC VERSION 2.0 TO GRADE TOXICITIES IN THIS STUDY!**

## APPENDIX D

### FACT-O, VERSION 4

#### FACT-O (Version 4)

Below is a list of statements that other people with your illness have said are important. Please circle or mark one number per line to indicate your response as it applies to the past 7 days.

PHYSICAL WELL-BEING		Not at all	A little bit	Some- what	Quite a bit	Very much
GP1	I have a lack of energy .....	0	1	2	3	4
GP2	I have nausea.....	0	1	2	3	4
GP3	Because of my physical condition, I have trouble meeting the needs of my family.....	0	1	2	3	4
GP4	I have pain .....	0	1	2	3	4
GP5	I am bothered by side effects of treatment .....	0	1	2	3	4
GP6	I feel ill .....	0	1	2	3	4
GP7	I am forced to spend time in bed.....	0	1	2	3	4
SOCIAL/FAMILY WELL-BEING		Not at all	A little bit	Some- what	Quite a bit	Very much
GS1	I feel close to my friends.....	0	1	2	3	4
GS2	I get emotional support from my family .....	0	1	2	3	4
GS3	I get support from my friends.....	0	1	2	3	4
GS4	My family has accepted my illness .....	0	1	2	3	4
GS5	I am satisfied with family communication about my illness.....	0	1	2	3	4
GS6	I feel close to my partner (or the person who is my main support) .....	0	1	2	3	4
Q1	Regardless of your current level of sexual activity, please answer the following question. If you prefer not to answer it, please mark this box  and go to the next section.					
GS7	I am satisfied with my sex life .....	0	1	2	3	4

